11.8 Additional Information Related to Pembrolzumab and Reporting

11.8.1 Definition of a Pembrolizumab Overdose for This Protocol and Reporting of Pembrolizumab Overdose to the Sponsor and to Merck

For purposes of this trial, an overdose of pembrolizumab will be defined as any dose of 1,000 mg or greater (5 times the indicated dose). No specific information is available on the treatment of overdose of pembrolizumab. Appropriate supportive treatment should be provided if clinically indicated. In the event of overdose, the subject should be observed closely for signs of toxicity.

If an adverse event³³ is associated with ("results from") the overdose of a Merck product, the adverse event³³ is reported as a serious adverse event, even if no other seriousness criteria are met.

If a dose of Merck's product meeting the protocol definition of overdose is taken without any associated clinical symptoms or abnormal laboratory results, the overdose is reported as a non-serious Event of Clinical Interest (ECI), using the terminology "accidental or intentional overdose without adverse effect."

All reports of overdose with and without an adverse event must be reported within 24 hours to the Sponsor and within 2 working days hours to Merck Global Safety. (Attn: Worldwide Product Safety; [contact])

11.8.2 Events of Clinical Interest

Reporting to Incyte

Selected non-serious and serious adverse events are also known as Events of Clinical Interest (ECI) and must be reported within 24 hours to Incyte.

All Serious Adverse Events ("SAE") required to be reported pursuant to the Protocol shall be provided to Incyte and its representatives by Institution or Principal Investigator within twenty-four (24) hours of learning of the event as well as any additional reports agreed upon by Institution or Principal Investigator and Incyte. SAE Reports will be sent to [contact]. By sending to this e-mail address, the Incyte Pharmacovigilance group will receive copies of the reports. This process will be tested

and established before the first patient is enrolled in the Study. Notwithstanding anything to the contrary herein, Institution will have the primary responsibility of reporting adverse events ("AE") to regulatory authorities.

For the time period beginning when the consent form is signed until treatment allocation/randomization, any ECI, or follow up to an ECI, that occurs to any subject must be reported within 24 hours to Incyte and within 2 working days to Merck Global Safety if it causes the subject to be excluded from the trial, or is the result of a protocol-specified intervention, including but not limited to washout or discontinuation of usual therapy, diet, placebo treatment or a procedure.

For the time period beginning at treatment allocation/randomization through 90 days following cessation of treatment, or 30 days following cessation of treatment if the subject initiates new anticancer therapy, whichever is earlier, any ECI, or follow up to an ECI, whether or not related to Merck product, must be reported within 24 hours to Incyte and within 24 hours to Merck Global Safety.

Events of clinical interest for this trial include:

- 1. an overdose of Merck product, as defined in Section 11.8.1 Definition of an Overdose for This Protocol and Reporting of Overdose to the Sponsor, that is not associated with clinical symptoms or abnormal laboratory results.
- 2. an elevated AST or ALT lab value that is greater than or equal to 3X the upper limit of normal and an elevated total bilirubin lab value that is greater than or equal to 2X the upper limit of normal and, at the same time, an alkaline phosphatase lab value that is less than 2X the upper limit of normal, as determined by way of protocol-specified laboratory testing or unscheduled laboratory testing.*

*Note: These criteria are based upon available regulatory guidance documents. The purpose of the criteria is to specify a threshold of abnormal hepatic tests that may require an additional evaluation for an underlying etiology.

12.0 CRITERIA FOR THERAPEUTIC RESPONSE/OUTCOME ASSESSMENT

12.1 Antitumor effect

All patients will undergo a baseline staging CT scan of the chest (with or without contrast), abdomen and pelvis (with or without contrast), and MRI of the affected area if deemed necessary by the treating physician. Response evaluations will occur at week 8 and every 8 weeks subsequently (± 1 week window) until week 56, and then less frequently at the discretion of the treating investigator.

Response and progression will be evaluated in this study using the international criteria proposed by the revised Response Evaluation Criteria in Solid Tumors (RECIST) guideline, version 1.1 (Primary response criteria).⁵⁴ Changes in the largest diameter (unidimensional measurement) of the tumor lesions and the shortest diameter in the case of malignant lymph nodes are used in the RECIST criteria.

In addition, patients will also be evaluated using the Immune-related Evaluation Response Criteria (irRECIST), which will not be used for treatment decisions (Secondary Response Criteria) and are discussed separately in section 12.12

In subjects who have initial evidence of progressive disease (PD) as per RECIST criteria or irRECIST criteria, it is at the discretion of the investigator to continue a subject on study treatment until confirmation of PD 4 weeks. This clinical judgment decision should be based on the subject's overall clinical condition, including performance status, clinical symptoms, and laboratory data.

Subjects will receive treatment if they are clinically stable as defined by the following criteria:

- Absence of signs and symptoms indicating PD.
- No decline in the Eastern Cooperative Oncology Group (ECOG) performance status
- Absence of rapid progression of disease
- Absence of progressive tumor at critical anatomical sites (e.g., cord compression)
 requiring urgent alternative medical intervention

Patients who decide to continue study therapy on protocol after initial radiolgic evidence of disease progression will need to provide written informed consent at the time of the decision to treat beyond initial evidence of progression of disease on study therapy.

12.2 Definitions

Evaluable for toxicity - Patients evaluable for safety analysis will include all patients who have received at least one dose of epacadsotat and pembrolizumab. Patients will be evaluable for toxicity from the time of their first treatment with epacadostat and pembrolizumab.

Evaluable for efficacy - Only those patients who have a measurable disease based on RECIST 1.1 criteria will be eligible for this study, as highlighted in Section 6.0. These patients will have their response classified according to the definitions stated below.

Only those patients who have measurable disease present at baseline, have received at least one cycle of the combination therapy, and have had their disease re-evaluated will be considered evaluable for response. (Note: Patients who exhibit objective disease progression prior to the end of cycle 1 will also be considered evaluable and determined to

Memorial Sloan Kettering Cancer Center IRB Number: 17-508 A(8)

Approval date: 07-May-2024

be non-responders. Note: one cycle of therapy consists of 21 days where the study therapy (epacadostat and pembrolizumab) is administered at the start of the cycle on day 1)

12.2.1 Disease Parameters

Measurable disease - Measurable lesions are defined as those that can be accurately measured in at least one dimension (longest diameter to be recorded for non-nodal lesions and short axis for nodal lesions) as >20mm by chest x-ray, as >10mm with CT scan or MRI, or >10mm with calipers by clinical exam. All tumor measurements must be recorded in millimeters (or decimal fractions of centimeters).

To be considered pathologically enlarged and measurable, a lymph node must be > 15 mm in short axis when assessed by CT scan (CT scan slice thickness recommended to be no greater than 5 mm). At baseline and in follow-up, only the short axis will be measured and followed.

Note: Tumor lesions that are situated in a previously irradiated area are not considered measurable unless there is evidence of progression after radiation therapy.

Non-measurable disease - All other lesions (or sites of disease), including small lesions (longest diameter <10mm or pathological lymph nodes with 10 to <15mm short axis) are considered non-measurable disease. Bone lesions, leptomeningeal disease, ascites, pleural/pericardia! effusions, lymphangitis cutis/pulmonitis, inflammatory breast disease and abdominal masses (not followed by CT or MRI), are considered as non-measurable.

Target lesions - All measurable lesions up to a maximum of 2 lesions per organ and 5 lesions in total, representative of all involved organs, should be identified as target lesions and recorded and measured at baseline. Target lesions should be selected on the basis of their size (lesions with the longest diameter), be representative of all involved organs, but in addition should be those that lend themselves to reproducible repeated measurements. A sum of the diameters (longest for non-nodal lesions, short axis for nodal lesions) for all target lesions will be calculated and reported as the baseline sum diameters. The baseline sum diameters will be used as a reference to further characterize any objective regression in the measurable dimension of the disease.

Non-target lesions - All other lesions (or sites of disease) including any measurable lesions over and above the 5 target lesions should be identified as non-target lesions and should also be recorded at baseline. Measurements of these lesions are not required, but the presence, absence or in rare cases unequivocal progression of each should be noted throughout follow-up.

12.3 Methods for Evaluation of Measurable Disease

All measurements should be taken and recorded in metric notation using a ruler or calipers. All baseline evaluations should be performed as closely as possible to the beginning of treatment and never more than 4 weeks before the beginning of the treatment.

The same method of assessment and the same technique should be used to characterize each identified and reported lesion at baseline and during follow-up portion of study. Imaging-based evaluation is preferred to evaluation by clinical examination unless the lesion³³ being followed cannot be imaged but are assessable by clinical exam.

Clinical lesions - Clinical lesions will only be considered measurable when they are superficial (e.g., skin nodules and palpable lymph nodes) and 10 mm diameter as assessed using calipers (e.g., skin nodules). In the case of skin lesions, documentation by color photography, including a ruler to estimate the size of the lesion, is recommended.

Chest x-ray - Lesions on chest x-ray are acceptable as measurable lesions when they are clearly defined and surrounded by aerated lung. However, CT is preferable.

Conventional CT and MRI - This guideline has defined measurability of lesions on CT scan based on the assumption that CT slice thickness is 5 mm or less. If CT scans have slice thickness greater than 5 mm, the minimum size for a measurable lesion should be twice the slice thickness. MRI is also acceptable in certain situations (e.g. for body scans).

Use of MRI remains a complex issue. MRI has excellent contrast, spatial, and temporal resolution; however, there are many image acquisition variables involved in MRI, which greatly impact image quality, lesion conspicuity, and measurement. Furthermore, the availability of MRI is variable globally. As with CT, if an MRI is performed, the technical specifications of the scanning sequences used should be optimized for the evaluation of the type and site of disease. Furthermore, as with CT, the modality used at follow-up should be the same as was used at baseline and the lesions should be measured/assessed on the same pulse sequence. It is beyond the scope of the RECIST guidelines to prescribe specific MRI pulse sequence parameters for all scanners, body parts, and diseases. Ideally, the same type of scanner should be used and the image acquisition protocol should be followed as closely as possible to prior scans. Body scans should be performed with breath-hold scanning techniques, if possible.

12.3.1 Primary Response Criteria (RECIST 1.1)

12.3.1.1 Evaluation of Target Lesions

Memorial Sloan Kettering Cancer Center IRB Number: 17-508 A(8)

Approval date: 07-May-2024

Complete Response (CR): Disappearance of all target lesions. Any pathological lymph nodes (whether target or non-target) must have reduction in short axis to <10 mm.

Partial Response (PR): At least a 30% decrease in the sum of the diameters of target lesions, taking as reference the baseline sum diameters.

Progressive Disease (PD): At least a 20% increase in the sum of the diameters of target lesions, taking as reference the smallest sum on study (this includes the baseline sum if that is the smallest on study). In addition to the relative increase of 20%, the sum must also demonstrate an absolute increase of at least 5 mm. (Note: the appearance of one or more new lesions is also considered progressions).

Stable Disease 1: Neither sufficient shrinkage to qualify for PR nor sufficient increase to qualify for PD, taking as reference the smallest sum diameters while on study.

12.3.1.2 **Evaluation of Non-Target Lesions**

Complete Response (CR): Disappearance of all non-target lesions and normalization of tumor marker level. All lymph nodes must be non-pathological in size (<10 mm short axis).

Non-CR/Non-PD: Persistence of one or more non-target lesion³³.

Progressive Disease (PD): Appearance of one or more new lesions and/or unequivocal progression of existing non-target lesions. Unequivocal progression should not normally trump target lesion status. It must be representative of overall disease status change, not a single lesion increase.

Although a clear progression of "non-target" lesions only is exceptional, the opinion of the treating physician should prevail in such circumstances, and the progression status should be confirmed at a later time by the review panel (or MSKCC Principal Investigator).

12.3.1.3 **Evaluation of Best Response**

The best response is the best response recorded from the start of the treatment until disease progression/recurrence (taking as reference for progressive disease the smallest measurements recorded since the treatment started). The patient's best response assignment will depend on the achievement of both measurement and confirmation criteria.

Table 18. Evaluation of Best Response - RECIST criteria

Target Lesions	Non- Target Lesions	New Lesions	Best Response	Best Response for This Category also Requires:
CR	CR	No	CR	4 wks. Confirmation
CR	Non-CR/ Non-PD	No	PR	
PR	Non-CR/ Non-PD	No	PR	4 wks. Confirmation
SD	Non-CR/ Non-PD	No	SD	documented at least once 4 wks. from baseline
PD	Any	Yes or No	PD	
Any	PD*	Yes or No	PD	no prior SD, PR or CR
Any	Any	Yes	PD	

^{*} In exceptional circumstances, unequivocal progression in non-target lesions may be accepted as disease progression.

Note: Patients with a global deterioration of health status requiring discontinuation of treatment without objective evidence of disease progression at that time should be reported as "symptomatic deterioration." Every effort should be made to document the objective progression even after discontinuation of treatment.

12.4 Confirmation of response

Complete or partial response may only be claimed if the criteria for each are met at a subsequent time point (4 weeks later) in studies with a primary endpoint that include response rate.

12.4.1 Special note on target lesions that become "too small to measure"

While on study, all lesions (nodal and non-nodal) recorded at baseline should have their actual measurements recorded at each subsequent evaluation, even when very small (e.g.

Memorial Sloan Kettering Cancer Center IRB Number: 17-508 A(8)

Approval date: 07-May-2024

2mm). However, sometimes, lesions or lymph nodes which are recorded as target lesions at baseline become so faint on CT scan that the radiologist may not feel comfortable assigning an exact measure and may report them as being "too small to measure". When this occurs, it is important that a value be recorded on the D2M form. If it is the opinion of the radiologist that the lesion has likely disappeared, the measurement should be recorded as O mm. If the lesion is believed to be present and is faintly seen but too small to measure, a default value of 5 mm should be assigned.

12.5 Not evaluable (NE)

When no imaging/measurement is done at all at a particular time point, the patient is considered not evaluable (NE) at that time point.

12.6 Early death

If the patient has no repeat tumor assessments following initiation of study therapy resulting from the death of the patient due to disease or treatment, it is considered early death.

12.7 Symptomatic Deterioration

Patients with global deterioration of health status requiring discontinuation of treatment without objective evidence of disease progression at that time be recorded as "symptomatic deterioration". Every effort should be made to document objective progression even after discontinuation of treatment.

12.8 Duration of response

Defined as the time measurement criteria are first met for CR/PR until the first date that recurrent or progressive disease is objectively documented (taking as reference for progressive disease the smallest measurement recorded on study).

12.9 Duration of stable disease

Measured from the start of the treatment until the criteria for progression are met, taking as reference the smallest sum on study (if the baseline sum is the smallest, this is the reference for calculation of PD).

12.10 Progression-Free Survival (PFS)

PFS is defined as the period from start of study treatment until recurrent or progressive of disease (POD) is objectively documented (taking as reference for progressive disease the smallest measurement recorded on study), death, or date of last study visit involving assessment of disease status.

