as long as patient is clinically benefitting, is tolerating the drug well and continues to meet all study treatment criteria.

The safety of the combination of epacadostat and pembrolizumab in patients with advanced sarcoma will be determined using CTCAE v4.03 criteria for toxicity assessment. Safety data will be collected for up to 90 days following the last dose of the study drugs. Therapy will be discontinued due to confirmed progression of disease or clinical progression, intercurrent illness that prevents further administration of treatment or intolerance of study treatment. Study personnel will attempt to collect survival status for all patients after the end-of-study visit every 3 months via telephone, email, or another method for up to 1 year.

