9.3 Duration of Therapy

Study treatment may continue until one of the following criteria applies:

Until a total of 35 cycles (approximately 2 years) of treatment has been administered as long as subjects are receiving benefit from treatment and have not had disease progression or met any criteria for study withdrawal outlined below

Clinical or radiographic disease progression as defined by RECIST 1.1. Patient may be allowed to continue treatment after progression if they are deriving clinical benefit (section 9.4).

Intercurrent illness that prevents further administration of treatment

Intolerance of study treatment

Patient decides to withdraw from the study

Physician decides to withdraw a patient from the study for a reason not listed here

Pregnancy in patient

The patient is lost to follow-up

Inability of the patient to comply with the requirement of the protocol for treatment or evaluation.

End of study, whichever occurs first.

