14.2 Secondary Endpoints

Secondary endpoints include:

1. Safety

Patients evaluable for safety analysis will include all patients who have received at least one dose of epacadsotat and pembrolizumab. Adverse events will be graded according to the NCI CTCAE v4.03, presented on an individual basis and summarized using descriptive statistics.

2. Survival

Progression free survival (PFS) rate at 24 weeks, median PFS, overall survival (OS) and progression-free survival intervals will be estimated using Kaplan-Meier methodology

3. Best Objective Response Rate by irRECIST

Best objective response rate (complete response + partial response) by 24 weeks by immune-related response criteria (irRECIST), of epacadostat in combination with pembrolizumab in patients with metastatic and/or locally advanced, sarcoma.

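### The 24-week PFS rate would be too high if patients who stop for clinical progression have no timely scan or death; a sensitivity estimate would bound this

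*Combined protocol and SAP*

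**What the plan says.** **PFS definition.** Section 12.10 runs PFS from the start of treatment "until recurrent or progressive of disease (POD) is objectively documented", or to "death, or date of last study visit involving assessment of disease status". The end dates stand in one list, and the text does not say which are events and which are censoring. The natural reading is that progression and death are events and the last disease assessment is a censoring date. Clinical progression is not in the list.

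**Stopping treatment.** Section 4.1 says: "Therapy will be discontinued due to confirmed progression of disease or clinical progression". Section 9.3 gives "Clinical or radiographic disease progression as defined by RECIST 1.1" as a reason for ending treatment.

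**Recording.** Section 12.7 covers "Patients with global deterioration of health status requiring discontinuation of treatment without objective evidence of disease progression" at that time and labels them symptomatic deterioration. It then adds: "Every effort should be made to document objective progression even after discontinuation of treatment". The note under the RECIST best-response table in Section 12.3.1.3 repeats the instruction. Neither place names a visit, an interval or a scan.

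**Imaging.** Section 12.1 and the notes to Table 5 put scans at week 8 and every 8 weeks to week 56. They do not say whether scans continue after treatment stops. The off-study column of Table 5 has no CT or MRI, and neither does the list of procedures about 30 days after the last dose in Section 13.0. Later contacts, every 12 weeks for up to 12 months, cover survival and new sarcoma therapy.

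**Analysis.** Section 14.2 makes "Progression free survival (PFS) rate at 24 weeks" a secondary endpoint estimated by Kaplan-Meier, with no censoring rule, target value or test. Section 2.0 specifies RECIST 1.1 and irRECIST for it.

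**The concern.** Kaplan-Meier assumes that a censored patient has the same future risk as those still under observation. A patient taken off treatment because of clinical decline is unlikely to meet that assumption. If such a patient is censored at the last assessment, a probable failure leaves the risk set without being counted, and the estimated rate can only move up.

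The plan already deals with this for response. Section 14.1 counts a patient whose assessment was missed because of progression or treatment-related toxicity as a non-responder. PFS has no matching rule.

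At stake is a named secondary objective in a single-arm trial of 30 patients, with no control group to share the error.

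**Working it through.** **1. The plan's own figures.** No figure is given for PFS. The only sizing figures belong to the response rule (30 patients, success at 6 or more responses). Exact binomial: P(X ≥ 6 | 30, 0.10) = 0.0732 and P(X ≥ 6 | 30, 0.30) = 0.9234, which agree with the stated 0.07 and 0.92 to two decimals. That rule does not use PFS.

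**2. What can happen to one patient.** Suppose a patient has a scan at week 8 and stops for clinical progression at week 12. There are three outcomes:
- A later scan shows progression: event on that date.
- The patient dies: event at death. This corrects the 24-week rate only if the death falls by week 24.
- Neither is recorded: censored at the last visit with a disease assessment, here taken as week 8.

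**3. Formula when all are censored.** Assumptions: scans at weeks 8, 16 and 24; the same risk in each interval; a share *s* of progressions that is clinical only, censored at the previous scan. The documents give neither *s* nor an expected PFS rate.

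Let the true 24-week rate be S. The chance of passing one interval is p = S^(1/3), and q = 1 − p. The fraction *s·q* leaves before the interval is counted, so the estimated chance of passing it is p / (1 − s·q). Over three intervals:

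estimate = S / (1 − s·q)³

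For S = 0.30: p = 0.6694, q = 0.3306.
- s = 10%: 0.30 / 0.9669³ = 33.2%
- s = 20%: 0.30 / 0.9339³ = 36.8%
- s = 30%: 0.30 / 0.9008³ = 41.0%

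A simulation of 400,000 patients with exponential progression gives 33.3%, 36.9% and 41.1%. At true rates of 20% and 40% it gives 22.8% to 29.9% and 43.2% to 51.2% over the same shares.

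**4. Check with 30 patients.** At a true rate of 30% there are 21 progressions by week 24, so shares of 10% to 30% mean about 2 to 6 patients. Take 11, 6 and 4 progressions in the three intervals, leaving 9 of 30 event-free. Let 3 be clinical only: 2 before week 8 (censored at baseline) and 1 between weeks 8 and 16 (censored at week 8).
- Week 8: 28 at risk, 9 events, factor 19/28
- Week 16: 18 at risk, 5 events, factor 13/18
- Week 24: 13 at risk, 4 events, factor 9/13

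Product = 19/56 = 33.9%. With 2, 5 or 6 such patients the result is 32.8%, 37.3% or 38.7%. Across true rates of 20% to 40%, the excess for 2 to 6 patients is about 2 to 11 points.

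**5. When some are captured.**
- All have progression or death recorded by week 24: the excess is zero.
- About half die by week 24 and the rest are censored (30 patients, as in step 4): the excess is about 1 to 4 points.
- Half are captured at the next scheduled scan: *s* in the formula is halved, giving 31.5%, 33.2% and 34.9% against a true 30%.
- None is scanned, but each counts at death, with an assumed median of 8 to 16 weeks after deterioration: simulation gives 33–34%, 35–38% and 37–42%. Deaths that come late help little, because many fall after week 24.

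**The case against.** The strongest reply is that the plan foresees the problem. Section 12.7 and the note under the best-response table both ask for objective progression to be documented after treatment stops, and the scan schedule is tied to study weeks rather than expressly to treatment. So a reader should not infer that these patients are left unassessed by design. This stands. It leaves a narrower gap: an instruction with no date, which neither Table 5 nor the lists in Section 13.0 put into effect.

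A reader might also infer that the PFS rate is biased upward as a matter of fact. The documents do not support that. The bias depends on how many patients have clinical progression only and no scan or death by week 24, and it may be nil.

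Three further points stand in part:
- Section 12.10 refers to a visit with a disease assessment, not to a scan. Sections 12.2.1 and 12.3 allow caliper measurement of superficial lesions, so some patients may be assessed at the off-study visit. In the 30-patient calculation, censoring at a later visit before the next scan left the 24-week estimate unchanged.
- Global deterioration is not always tumour progression. The true rate in the working treats every such stop as progression, so counting all of them as events could err downward. This is a reason to show two rates rather than replace one.
- The objective-only definition fits the RECIST wording in Section 2.0. It is a legitimate main estimate and not an error.

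On size, the binomial standard error at 30% with 30 patients is √(0.3 × 0.7 / 30) = 8.4 points. Shifts of 3 to 7 points (shares of 10% to 20%) lie within one standard error. A one-directional shift is nevertheless not described by the confidence interval.

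**Conclusion.** The point holds in a conditional form. Section 12.10 omits an outcome that stops treatment, no dated scan follows the stop, and no rule says how such patients enter the PFS analysis. Any resulting error in the 24-week rate is upward relative to a rate that counts clinical progression as failure.

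With a true rate of 30% and assumed clinical-only shares of 10% to 30%, the estimate is about 33% to 41% if all these patients are censored. It is lower if timely scans or deaths capture some of them, and correct if all are captured by week 24. The shares, the true rate and the constant risk are assumptions.

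A reader might go further and infer that the trial's conclusion is affected. It is not: the decision rests on 6 or more responses among 30 patients. PFS has no test, target or stated benchmark in this plan. This is a cheap improvement to a secondary estimate.

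**What to change.** Keep the objective-only RECIST 1.1 rate as the main 24-week PFS estimate. In Section 14.2 add one sensitivity estimate in which a treatment stop for symptomatic deterioration or clinical progression counts as an event on the documented stop date. Show it beside the main rate, with the number of such patients. A sentence in Section 12.10 stating which end dates are events and which are censoring would make the comparison readable.

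**Cost.** One extra line of analysis, with no added visit or scan. Section 13.0 already requires the reason for and date of removal from study. Its list of reasons does not name clinical progression, and removal from study may not coincide with stopping treatment, so the team should confirm that the database holds that reason and the treatment-stop date.

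**Downside.** The second estimate relies on investigator judgement in an open-label trial and may count some deterioration that is not tumour progression. The two rates should be read as a range.
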